6.18 Treatment Past Disease Progression

Clinical evidence suggests that a minority of patients treated with immunotherapies will derive clinical benefit after an initial assessment of PD. For patients in this study, if initial PD based on RECIST v.1.1 occurs, treatment may continue according to the protocol-specified regimen provided all of the following criteria are met:

- Absence of signs or symptoms indicating clinically significant disease progression
- No decline in ECOG performance status

- No associated impending threat to vital organ function (eg, cord compression, liver function) or indication for immediate palliative therapy (eg, radiation for cord compression)

Patients continuing treatment beyond the initial protocol-specified RECIST v.1.1 progression must provide separate consent to continue IMCnyeso treatment. Disease assessments will continue to be performed according to the schedule in Table 7-2. The size of any new, measurable lesions is to be reported in the eCRF.

Patients treated beyond initial disease progression who experience further progression, defined as an additional ≥ 5 mm increase in tumor burden (sum of diameters of both target and new lesions) and/or identification of additional new lesions, at least 4 weeks after the initial PD assessment ([Seymour, 2017](#)), must permanently discontinue study treatment.

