9.5.2 Phase II: Efficacy

In Phase II, the primary endpoint is the best overall response (BOR). The primary summary measure is ORR, defined as the proportion of patients with a BOR of complete response (CR) or partial response (PR) based on local Investigator assessment, as defined in RECIST v.1.1. ORR will be analyzed separately for the Phase II cohorts. Confirmation of response is required for declaring a PR or CR as the BOR. A confirmed response is defined as a CR or PR followed by a CR or PR at least 4 weeks later. ORR will be summarized with accompanying 95% confidence interval.

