3.2.2 Secondary Endpoints

For both phases, the following will be analyzed:

- Progression-free Survival (PFS)
- Duration of Response (DoR) by RECIST v1.1
- Overall Survival (OS)
- Serum PK parameters (e.g. AUC, Cmax, Tmax, $t_{1/2}$) after single and multiple doses
- The incidence of anti-IMCnyeso antibody formation

For Phase I only, the following secondary endpoint will also be analyzed:

- Best Overall Response (BOR)

For Phase II only, the following secondary endpoints will also be analyzed:

- Incidence and severity of AE and SAE
- Changes in laboratory parameters, vital signs, and ECGs
- Dose interruptions, reductions, and discontinuations

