9.1.1 Objective Response Rate

The primary summary measure of Best Overall Response (BOR) is the ORR, defined as the proportion of patients with a best overall response of CR or PR based on local investigator

assessment, as defined in RECIST v.1.1. The denominator in the calculation of the ORR will be the number of patients with measurable disease at baseline in the FAS / PPS as appropriate. All these patients included in the denominator will be categorized by their BOR (CR, PR, SD, PD, NE).

Confirmation of response is required for declaring PR or CR in the ORR. A confirmed response is defined as a CR or PR followed by a CR or PR at least 4 weeks later (allowing a window, this will need to be at least 3.5 weeks after the original assessment). Patients who have a PD event (progression or death) immediately after 2 or more consecutive missed/non-evaluable tumor assessment visits, will have a BOR of NE. Specifically for patients who die with no evaluable follow-up tumor assessments or no evaluable baseline assessment, if the death occurs immediately after the first 2 scheduled scans, then the BOR will also be NE. An exception to this rule is if the patient (with no evaluable follow-up tumor assessments or no evaluable baseline assessment) dies within 2 visits of first dose of study drug, then the BOR will be PD (for death in the absence of progression).

Tumor response will be determined per local investigator's assessment, according to RECIST v.1.1

Individual lesion measurements and overall response assessments will be listed by patient and assessment date. Best overall response per RECIST v.1.1 will be listed and tabulated. Change in tumor size for individual patients will be shown in spider plots. Duration of Treatment, Tumor Response and Response Duration will be shown in swimmer plots. Best overall change in tumor size for individual patients will be shown in waterfall plots and may be repeated at 13 and 26 weeks (Cycle 3 and Cycle 6).

Best overall response analysis per RECIST v.1.1 will be repeated for PPS. BOR will be summarized for overall and by Synovial cohort.

ORR and DCR (CR + PR + stable disease [SD]) will be summarized with accompanying 95% Clopper-Pearson's confidence interval. A patient is eligible for an assessment of stable disease only after 16 weeks from day of first dose. Any SD assessed before 16 weeks will not be counted as SD in the DCR.

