DoR and time-to-response for patients who experience a CR or PR at any time on study will be listed by patient. Duration of response is the time in months from the date of first documented objective response until the date of progression or death (whichever occurs first). If a large proportion of patients achieves a response (e.g. 5/10), Kaplan-Meier plots for DoR will also be produced, and the median DoR will be estimated. The time-to-response is defined as the time from first dose to their first CR or PR.

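### Duration of response and time-to-response are defined for any CR or PR, without the confirmation that ORR requires and with no stated cut at first progression

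*SAP*

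**What the plan says.** **Responders for the primary endpoint.** SAP 9.1.1: "Confirmation of response is required for declaring PR or CR in the ORR". Protocol 9.5.2 says the same of BOR: "Confirmation of response is required for declaring a PR or CR as the BOR". The definition is: "A confirmed response is defined as a CR or PR followed by a CR or PR at least 4 weeks later". The SAP adds a window that accepts 3.5 weeks.

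**Responders for DoR and time-to-response.** The following paragraph of SAP 9.1.1 reads: "DoR and time-to-response for patients who experience a CR or PR at any time on study will be listed by patient". Protocol 9.6.1 carries the same sentence, so the SAP inherits it. The SAP then gives two definitions: "Duration of response is the time in months from the date of first documented objective response until the date of progression or death" and "The time-to-response is defined as the time from first dose to their first CR or PR". None of these sentences mentions confirmation or limits responses to the time before first progression.

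**Status and outputs.** SAP 3.2.2 lists "Duration of Response (DoR) by RECIST v1.1" as a secondary endpoint in both phases, in line with Protocol Table 4-1. Time-to-response is in neither list. The outputs are patient listings and swimmer plots. A Kaplan-Meier plot and median DoR follow only if a large share of patients respond, with 5 of 10 given as the example.

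**After progression.** Protocol 6.18 covers patients with initial RECIST v1.1 progression: "treatment may continue according to the protocol-specified regimen provided all of the following criteria are met". Disease assessments then continue on the regular schedule.

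**The concern.** DoR is normally read as describing the patients counted as responders in the ORR. Here the two sets are defined by different rules within one SAP section. A programmer who follows the DoR sentence as written would include a patient with a single unconfirmed PR, who is not a responder for the ORR. The number of patients with a DoR could then exceed the ORR numerator. The extra patients would tend to have short durations, because a response lost at the next scan is exactly what fails confirmation.

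Two further points are left open. The Kaplan-Meier trigger refers to patients who achieve a response without saying whether confirmed or any responses are counted. And because treatment and scans may continue after first progression, the phrase about any time on study does not rule out a response first seen after progression. DoR as defined runs from response to progression, so it has no sensible value for such a patient, while time-to-response has no progression bound at all.

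**Working it through.** **1. The plan's own efficacy figures.** No figure is stated for DoR. The nearest computed figure is the Simon design (Protocol 9.9.2, SAP 4.1): 9 patients, stop at 0 responses, up to 24 in total, at least 3 responses, 5% versus 20%, type I error 10%, type II error 20%. The exact probability of passing is the sum over x = 1 to 9 of P(X1 = x) × P(X2 ≥ 3 − x), with X1 ~ Bin(9, p) and X2 ~ Bin(15, p).

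- p = 0.05: 0.0931, within 0.10.
- p = 0.20: 0.8047, meeting 0.80.
- Early stop at p = 0.05: 0.95^9 = 0.630.

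The design reproduces. It rests on ORR, which already requires confirmation, so nothing below alters it.

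**2. Scan-driven durations.** Inputs: scans every 8 weeks to Week 40, then every 12 weeks (Protocol Table 7-2); 30.4375 days per month (the SAP's divisor). Months = weeks × 7 / 30.4375.

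| Pattern | Weeks | DoR (months) |
|---|---|---|
| Response, progression at next scan, 8-week schedule (unconfirmed) | 8 | 56 / 30.4375 = 1.84 |
| Same, 12-week schedule (unconfirmed) | 12 | 84 / 30.4375 = 2.76 |
| Response, confirmed at next 8-week scan, progression at the scan after | 16 | 112 / 30.4375 = 3.68 |

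The last row is the shortest confirmed DoR that scheduled 8-weekly scans can produce. An unscheduled scan, visit windows or a death could shorten it.

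**3. Effect on a median, illustration only.** Assume three confirmed responders with DoR of 24, 32 and 40 weeks, and add unconfirmed responders at 8 weeks each. These durations are assumed; the documents give none.

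| Unconfirmed added | Patients with a DoR | Median (weeks) | Median (months) |
|---|---|---|---|
| 0 | 3 | 32 | 7.36 |
| 1 | 4 | 28 | 6.44 |
| 2 | 5 | 24 | 5.52 |
| 3 | 6 | 16 | 3.68 |

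**4. How likely is the Kaplan-Meier output?** At the 20% target rate, P(at least 5 of 10) = 0.033 and P(at least 12 of 24) = 0.001 (exact binomial). The expected output is therefore the listing.

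**5. A response after progression.** With progression at Week 8 and a PR at Week 16, the DoR definition gives (8 − 16) × 7 / 30.4375 = −1.84 months. This shows that the definition does not fit the case. The plan does not specify such a value as an output.

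**The case against.** The sentence about a CR or PR at any time governs a listing. The Kaplan-Meier sentence is separate, conditional, and does not repeat that phrase. The DoR start date refers to an objective response, in a section on objective response rate, just after confirmation has been required, so it could be read as the confirmed response. The SAP also lists overall response by patient and assessment date, so a reader could see which responses were confirmed. All of this stands, and it limits the consequence. It does not settle the rule: two readings of a listed secondary endpoint remain, and the literal one is the wider set.

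A reader might infer that the plan tells the analyst to count responses after progression, or that it will produce negative durations. The documents do not support that. Protocol 6.18 permits treatment and scans past progression but defines no response category there. DoR is by RECIST v1.1 and ends at progression, which presupposes that response came first. Under Protocol Table 13-4, an assessment with a new lesion has an overall response of progression whatever the target lesions show. The SAP's ORR text states no cut at first progression either, so on this point the silence is shared and is not a mismatch between DoR and ORR.

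A reader might also infer that the Kaplan-Meier median definitely uses every one-scan responder. The text leaves that open. Finally, extra short durations would lower the median, so the wider set would not flatter the drug.

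**Conclusion.** The concern holds as a definitional mismatch. As written, DoR and time-to-response are not restricted to the confirmed responders who make up the ORR. The DoR count can therefore exceed the ORR numerator, and the added patients can have durations near 1.84 months where a confirmed response would show at least about 3.68 months on scheduled 8-weekly scans. Which count triggers the Kaplan-Meier analysis is unstated. Responses after first progression are an ambiguity only.

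The practical reach is modest. One secondary endpoint (DoR) and one descriptive measure (time-to-response) are affected, mainly through listings and swimmer plots, with a median only if about half of patients respond. The size of any shift in that median depends on assumed durations and on the number of unconfirmed responders, neither of which the documents give. It would be wrong to infer that the primary result is at risk: ORR, the Simon rule, the sample size and the error rates are untouched.

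**What to change.** In SAP 9.1.1:

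- State that DoR (secondary endpoint) and time-to-response (descriptive) are computed only for patients with a confirmed CR or PR first documented before first RECIST v1.1 progression, dated from the first assessment of the confirming pair.
- Count the same confirmed responders for the Kaplan-Meier trigger.
- List unconfirmed responses, and any first seen after progression, separately.

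Because Protocol 9.6.1 carries the wider sentence, record the departure in SAP Section 12.

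The cost is a few sentences and a filter in the programming. No new data or scans are needed.

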9.2 Secondary Efficacy Endpoints

9.2.1 Progression-free Survival

PFS is defined as the time from first dose until the date of objective progression, or death from any cause, whichever occurs first. Patients who progressed or died immediately after two or more missed scheduled tumor assessments will be censored at date of last adequate assessment with evidence of no progression. Patients who have not progressed or died at the time of analysis will be censored at the time of the latest date of assessment from their last evaluable RECIST 1.1 assessment. These censoring rules apply regardless of what concomitant medications may have been taken or if the patient discontinued treatment prior to their last assessment. A sensitivity

analysis may be performed if subjects without objective disease progression receive a new anti-cancer therapy potentially affecting their results. In this analysis such patients will then be censored at the date of the last adequate response assessment prior to the new anti-cancer therapy.

$PFS \text{ (months)} = (\text{Event date} - \text{date of first dose} + 1) / 30.4375$

The PFS will be presented graphically using Kaplan-Meier plots including all patients treated at the MTD or RP2D and by overall and Synovial cohort. Median PFS time and the proportion of patients who are progression-free at 3, 6, 9 and 12 months will be estimated for each group. To note, the 95% confidence interval will be calculated using “conftype = loglog” option within the Proc Lifetest procedure in SAS software.

PFS per RECIST v.1.1 will be listed by patient and tabulated.

PFS per RECIST v.1.1 will be repeated for the PPS for Phase II.

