Figure 6-2: Schematic Illustration of a 2-Step IPE Regimen

Rules for the 2-step IPE regimen are as follows:

- The initial target dose level must be a permitted escalation step based on BLRM output and the consensus of the SST
- The initial target dose level must not exceed the 1-step dose-escalation MTD (if established)
- The C1D8 dose level must be at least one dose level below the initial target dose, and must be a dose level that has been evaluated in ≥ 3 patients using a fixed-dose or 1-step IPE regimen, with a decision to escalate based on the BLRM output and SST review of all available relevant data
- Escalation of the target dose in subsequent cohorts may proceed as in the main and 1-step dose escalation:
 - Separate MTD/RP2D may be identified using fixed-dose, 1-step IPE, and 2-step IPE regimens
 - DLT will be attributed to the dose level of the most recently administered dose prior to onset of the DLT (eg, a DLT with onset on C1D4 would be attributed to the C1D1 dose level, while a DLT with onset on C1D10 would be associated to the C1D8 dose level)
- The dose levels for C1D1 and C1D8 remain fixed for all subsequent cohorts
- Patients receiving 2-step IPE must receive the C1D1 and C1D8 doses prior to receiving the target dose
- If a 2-step IPE regimen is evaluated in Phase I, it may be selected for further evaluation in Phase II

An example of how IPE might be implemented is shown in [Figure 6-3](#).

[figure not shown]

Figure 6-3: Representative Escalation Path Incorporating IPE

IPE = intra-patient escalation.

Actual dose levels will be determined using BLRM and must be approved by SST. In this scenario, after 3 patients were enrolled in Cohort 4 and completed DLT evaluation, the recommended next dose per BLRM was 195 mcg. The SST determined that the 195 mcg dose would be better tolerated using a 2-step escalation regimen, and so Cohort 5 was opened with a dose of 30 mcg on C1D1, 100 mcg on C1D8, and 195 mcg as the target dose (weekly starting on C1D15).

In addition, a patient who is enrolled in a lower dose cohort may move to a higher dose cohort once all the following criteria are met:

- The patient has completed at least 3 cycles of treatment
- The patient did not experience any DLT or any \geq Grade 3 treatment-related toxicity
- The patient does not have any ongoing \geq Grade 2 treatment-related toxicity
- The higher dose cohort has completed SST review with a decision to escalate or was determined to be the MTD/RP2D

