7.2 Treatment Period Schedule

The treatment period starts with Day 1 of Cycle 1 (C1D1). A treatment cycle is defined as 28 days for the purposes of scheduling procedures and evaluations.

Any assessments required on C1D1 that are also performed as part of Screening do not need to be repeated on C1D1 if the data were obtained 72 hours prior to the first dose of study treatment. For subsequent visits, pregnancy testing may be performed up to 72 hours prior to dosing and other safety assessments may be performed up to 24 hours prior to dosing.

During the study visits, all tests and/or procedures should occur on schedule whenever possible. A visit window of ± 7 days (with a minimum of 7 days between doses of IMCnyeso) is allowed unless otherwise indicated in the protocol. If study drug infusions are delayed, the assessments associated with those infusions should be rescheduled accordingly. However, the timing of protocol-specified radiological assessments should be calculated in weeks using C1D1 as reference and should not be adjusted because of delays in treatment.

Assessments required during the treatment period are presented by visit in [Table 7-2](#). For patients receiving IPE, follow the alternate Cycle 1 schedule provided in [Section 13.4](#). Assessments marked “X” should be performed prior to dosing. Assessments that are to be performed at multiple timepoints are marked with the number of timepoints (including optional timepoints, if applicable) for the visit (eg, 2 \times is twice) and details of the timepoints are provided in the footnote. Additional details regarding the assessments are provided in [Section 7.4](#). Please refer to [Section 6](#) for dosing details. Patients will continue treatment until they meet criteria for discontinuation, as described in [Section 6.16](#).

Table 7-2: Schedule of Treatment Period Assessments

Procedure	Cycle 1						Cycle 2				Cycle 3				Later Cycles			
Day of Cycle	1	2	8	9	15	22	1	8	15	22	1	8	15	22	Visits on Days 1, 8, 15, and 22			
Adverse events	X	X	X	X	X	X	X	X	X	X	X	X	X	X		X		
Concomitant medications	X	X	X	X	X	X	X	X	X	X	X	X	X	X		X		
Safety Assessments																		
Complete physical examination	X																	
Abbreviated physical examination			X		X	X	X	X	X	X	X	X	X	X		D1 of each cycle		
Weight	X						X				X						D1 of each cycle	
Vital signs	~14x	~14x		3x	3x	3x	3x	3x	3x	3x	3x	3x	3x	3x		3x each dosing day		
12-lead ECG (single)	2x						2x				2x					2x on C4D1, C5D1, and C6D1		

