9.2 Analysis Sets

9.2.1 Full Analysis Set

The full analysis set (FAS) comprises all patients who received at least 1 full dose or partial dose of IMCnyeso. Patients will be analyzed according to the planned treatment. The FAS will be used for all listings of raw data, demography and baseline characteristics. Unless otherwise specified, the FAS will be the default analysis set used for analyses.

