9.6 Secondary Analysis Variables

9.6.1 Efficacy

Analysis of efficacy endpoints will be performed using the FAS unless otherwise noted. For all efficacy parameters, data will be listed, summarized, or analyzed by treatment group for the Phase I dose escalation and separately for the Phase II expansion cohorts.

Individual lesion measurements and overall response assessments will be listed by patient and assessment date. Best overall response per RECIST v.1.1 will be listed and tabulated. Best overall change in tumor size for individual patients will be shown in waterfall plots.

PFS and OS will be listed by patient. PFS will be presented graphically using Kaplan-Meier plots including all patients treated at the MTD or RP2D and by disease group. Median PFS time and the proportion of patients who are progression-free at 3, 6, 9, and 12 months will be estimated for each group. Similarly, OS will be presented graphically using Kaplan-Meier plots including all patients treated at the MTD or RP2D and by disease group. Median OS time and the proportion of patients who are alive at 3, 6, 9, and 12 months will be estimated.

DoR and time-to-response for patients who experience a CR or PR at any time on study will be listed by patient. If a large proportion of patients achieve a response (eg, 5/10), Kaplan-Meier plots for DoR will also be produced, and the median DoR will be estimated.

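### Patients moved up to the MTD/RP2D bring time accrued on a lower dose into its PFS curve (and the protocol's OS curve), and the SAP does not say whether they belong there

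*SAP*

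**What the plan says.** **Who may move.** Protocol 6.10.1 provides that "a patient who is enrolled in a lower dose cohort may move to a higher dose cohort once all the following criteria are met". One criterion is "The patient has completed at least 3 cycles of treatment". Another is "The higher dose cohort has completed SST review with a decision to escalate or was determined to be the MTD/RP2D", so the destination may be the RP2D itself. The other criteria concern toxicity. None requires the patient to be free of progression, and protocol 6.18 allows dosing past RECIST progression under conditions.

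**Who is in the curves.** For PFS, SAP 9.2.1 says "The PFS will be presented graphically using Kaplan-Meier plots including all patients treated at the MTD or RP2D", and protocol 9.6.1 has the same definition. For OS, protocol 9.6.1 says "OS will be presented graphically using Kaplan-Meier plots including all patients treated at the MTD or RP2D". SAP 9.2.2 says OS is handled like PFS, but its own plot sentence refers to the Phase II FAS and PPS.

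**When the clock starts.** SAP 9.2.1: "PFS is defined as the time from first dose until the date of objective progression", or death if earlier. SAP 9.2.2 also starts OS at first dose. Neither section resets the clock at the first RP2D dose, uses delayed entry, or excludes movers. Estimates are planned at 3, 6, 9 and 12 months.

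**What else bears on grouping.** Protocol 9.2.1 says of the FAS: "Patients will be analyzed according to the planned treatment". SAP 4.3.2 groups Phase I FAS patients by planned treatment or by the dose groups of its Table 2. SAP 4.2.1 recognises patients who enter more than one cohort, but covers them only in baseline-type summaries and a listing of escalated patients.

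**The concern.** Selection into the curve depends on something that happens after the clock has started. A patient can join the MTD/RP2D group by moving up only if still alive and on treatment after three cycles, yet those cycles count as follow-up in the RP2D curve. For survival this is the classic immortal-time problem.

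For PFS the same time is misattributed, but a mover may bring in either progression-free months or a progression that occurred before any RP2D dose. In both cases the curve describes something other than outcome on the RP2D.

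At stake is the reported picture of PFS and OS at the RP2D, above all the 3-month estimate, which falls almost wholly within the lower-dose period for a mover. A related but smaller matter arises in the Phase I tables by planned dose group, where a response first seen after the move is credited to the original dose without any mark.

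**Working it through.** The documents give no PFS or OS assumption, so there is no figure of the plan's to reproduce. The medians and mover counts below are assumptions.

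**Inputs from the documents**
- At least 3 cycles before a move (protocol 6.10.1).
- Cycle length: "A treatment cycle is defined as 28 days for the purposes of scheduling procedures and evaluations" (protocol 7.2).
- 30.4375 days per month (SAP 9.2.1).
- At least 6 Phase I patients at the RP2D (protocol 6.11), and up to 24 per Phase II cohort (protocol 9.9.2). Protocol 9.1 allows the two phases to be pooled at the RP2D.

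**Step 1: time before the move.** 3 × 28 = 84 days, and 84 / 30.4375 = 2.76 months. That is 2.76 / 3 = 92% of the way to the 3-month estimate.

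**Step 2: PFS, movers progression-free at the move.** Assume exponential PFS with the same hazard at every dose and a move at exactly 84 days, so S(t) = 0.5^(t/median). With a 2-month median:
- Starter: S(3) = 0.5^(3/2) = 0.354.
- Mover: 0.5^((3 − 2.76)/2) = 0.920.
- 10 starters and 3 movers: (10 × 0.354 + 3 × 0.920) / 13 = 0.48, against a true 0.35.

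**Step 3: PFS, some movers already progressed.** Such a mover has an event before 3 months and adds nothing to the numerator.
- One of three: (10 × 0.354 + 2 × 0.920) / 13 = 0.41.
- Two of three: (10 × 0.354 + 1 × 0.920) / 13 = 0.34, just below the true 0.35.

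With a 3-month median, 6 starters and 4 movers, the sign also changes at about half: two of four with prior progression gives 0.489 against a true 0.50.

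**Step 4: other assumptions, 3-month estimates, PFS movers progression-free**

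| Endpoint, assumed median | Starters + movers | True | As written |
|---|---|---|---|
| PFS, 3 months | 6 + 4 | 0.50 | 0.68 |
| PFS, 3 months | 24 + 4 | 0.50 | 0.56 |
| OS, 9 months | 6 + 4 | 0.79 | 0.87 |
| OS, 9 months | 24 + 4 | 0.79 | 0.82 |

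For 2 to 6 movers beside 6 starters, the 3-month estimate rises by 9 to 28 points for PFS (medians 2 to 4 months) and 4 to 13 points for OS (medians 6 to 12 months). For 4 movers beside 24 starters the rises are 5 to 8 and 2 to 4 points. The bias shrinks by 12 months: with 6 + 4, PFS (3-month median) is 0.085 against 0.062, and OS (9-month median) is 0.434 against 0.397.

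**Step 5: does the fix remove it?** In a simulation of 8,000 runs for the four rows above, using starters only returned 0.50 for PFS and 0.79 for OS. Delayed entry and resetting the clock did the same to within 0.01.

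**Limit of the illustration.** Scheduled scans fall at weeks 8 and 16, so observed progressions will cluster there rather than follow a smooth exponential.

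**The case against.** The strongest reply is that the plan already keeps movers out. Efficacy is analysed on the FAS, the FAS follows planned treatment, and the planned Phase I Kaplan-Meier figures are titled as FAS outputs. Where the SAP wants selection by RP2D dose actually received, it creates a separate set (SAP 4.3.4) and uses it for safety. A programmer could reasonably leave movers in their original group. This stands as a possible reading, but it does not settle the matter: the curve definition is the more specific text and selects on treatment given. The two rules produce different curves, and nothing says which prevails.

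Three further objections stand and limit the point:
- **OS.** The SAP's own OS plot sentence concerns Phase II, whose patients are enrolled and treated at the RP2D. The OS part therefore rests on protocol 9.6.1 and on the SAP's statement that OS is handled like PFS.
- **Direction for PFS.** A reader might infer that RP2D PFS must be inflated. The documents do not support that, because patients with prior progression may be moved up.
- **Size.** The number of movers is unknown, and pooling with Phase II dilutes their effect.

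On responses, assessments are listed by patient and date, and swimmer and spider plots are planned. Timing relative to the move could be recovered, so that part needs only a flag.

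**Conclusion.** The point holds as a defect in how the MTD/RP2D curves are defined. As written, they include movers and count at least 84 days of lower-dose time as RP2D time.

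- **OS, as defined in protocol 9.6.1:** movers cannot contribute a death before day 84, so the early estimate can only be raised.
- **PFS:** the 3-month estimate is raised if movers were progression-free at the move, and the bias shrinks or reverses as more of them had already progressed.

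All sizes rest on assumed medians, equal hazards across doses, and assumed mover counts. If nobody moves to the RP2D, there is no effect.

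A reader might go further and infer that the choice of RP2D or the Phase II go/no-go is compromised. The documents do not support either. An RP2D curve exists only once the RP2D has been named, so it cannot have driven that choice. The Phase II decision uses the Simon rule on ORR. PFS and OS are secondary and descriptive, and SAP section 4 plans no hypothesis tests. The conflict between the two grouping rules should still be resolved before these curves are produced.

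**What to change.** In SAP 9.2.1 and 9.2.2 and protocol 9.6.1, state that MTD/RP2D Kaplan-Meier estimates include only patients whose first assigned regimen was the MTD/RP2D. Selecting on the assigned regimen also keeps in patients whose RP2D regimen begins with lower step-up doses.

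State that patients moved up under protocol 6.10.1 stay in their original planned dose group, in line with the FAS rule, and are listed with the date of the move. Flag any response first seen after the move with the dose at onset.

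The cost is a few sentences and one derived date, which the planned listing of escalated patients can carry. The downside is that the curves lose the few moved-up patients.
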